**14.0 Data Analysis**

**14.1 Analysis of Primary Objective**

Actuarial progression-free survival will be determined using the product-limit method of Kaplan and Meier. We will compare unadjusted median PFS between the 2 arms using a log-rank test. We will also use a proportional hazards model to compare progression-free survival between the two groups, adjusting for key covariates such as age, performance (ECOG) status, response to initial systemic therapy vs stable disease, the presence or absence of brain metastases, PD-L1 expression (< 1% vs > 50%), tumor histology (adenocarcinoma vs non-adenocarcinoma), number of disease sites treated (1-3 sites vs 4-6 sites vs 7-8 sites) and length of time between date of first chemotherapy-immunotherapy treatment and randomization date..

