## SCHEMA

\*Enrollment may occur after 4 cycles of standard of care systemic therapy (usually this will consist of combination chemo immunotherapy, but in some cases may be chemotherapy or immunotherapy alone). Neither enrollment nor randomization may occur more than 180 days from the first day of cycle 1 of systemic therapy. Protocol directed therapy should occur within 21 days of randomization (i.e. The start of RT or the resumption of maintenance io)

\*\* If a PET has been performed within 30 days of enrollment with no evidence of progression per RECIST v1.1, then this scan may be used and does not have to be repeated prior to randomization  
 If an MRI brain has been performed within 90 days of enrollment with no evidence of progression per RECIST v1.1, then this scan may be used and does not have to be repeated prior to randomization

\*\*\* Treatment of CNS disease with stereotactic radiosurgery or resection as appropriate per CNS team may take place prior to completion of first line chemotherapy, for stratification purposes this will still count as 1 site of disease

† Randomization will be stratified by number of metastatic sites (1-3, 4-6, or 7-8)

†† Total maintenance immunotherapy includes any maintenance therapy given prior to randomization

Treatment of non-squamous histology may include concurrent pemtrexed with immunotherapy consolidation

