**If randomized to continued maintenance immunotherapy alone:**

Patients will begin or resume maintenance immunotherapy no later than 21 days following randomization.

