## 13.0 Statistical Considerations

### 13.1 Power and Sample size

Based on previously published research and clinical experience, the predicted median progression-free survival (PFS) of patients treated with consolidation immunotherapy without SBRT is roughly 8 months measured from date of first chemo-immunotherapy treatment. We estimate that, considering this 8 month median survival in the “control” arm, with our projected sample size of 112 patients (randomized 2:1 to SBRT + immunotherapy vs immunotherapy alone), and considering a two-sided alpha of 0.05 and power of 0.80, that we will be able to detect a median survival of approximately 15 months from start of chemo-immunotherapy in the SBRT + immunotherapy arm. This calculation assumes a 54 month accrual period and a 5 year total follow-up period. This difference in median survivals (8 months vs 15 months) corresponds to a hazard ratio of 0.53. Randomization will be stratified by number of metastatic sites (1-3, 4-6, or 7-8.)

Given the design of this trial, not all enrolled patients will be eligible for subsequent randomization. We estimate that ~10% may have evidence of progression of disease on restaging with PET/MRI. Such patients would remain on study, but will only be followed for survival. Given this potential for a 10% decrease in randomizable patients, the final number needed to enroll is 125, in order to randomize 112.

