**14.2 Analysis of Secondary Objective**

The proportions with local control (LC) of SBRT-treated lesions, and overall survival (OS) parameter estimates, both secondary outcomes, will be first examined in simple univariate and bivariate analyses (e.g., means, medians, 85% confidence intervals around key parameter estimates.). LC will be assessed only in patients with at least 4-months of radiographic follow -up. The reason for specifying a minimum of 4 months follow-up to score LC was to avoid uncertainty associated with early transient radiographic changes within the high dose region; patients who died without a minimum of 4 months post-SBRT imaging study follow-up are not considered evaluable for LC but are evaluable for PFS and OS.

Data will be collected for planned subset analysis of in-field local control of irradiated sites, progression-free and overall survival according to (1) tumor histology (adenocarcinoma vs other histology) and (2) response to initial chemotherapy (response vs stable disease).

In all randomized patients, time to progression at known sites of disease, as well as time to development of new disease sites, and number of new disease sites will be collected.

Overall survival comparison between the two randomized groups will be assessed with methods analogous to PFS described above in 13.1. Additionally, we will also examine OS in the group of patients who were enrolled but not randomized; however, we will not conduct statistical comparisons of this group with either randomized group.

All safety measures, including acute and late toxicity, will be reported using descriptive statistics (mean, median, SD, proportions, and 95% confidence intervals). This will include calculating frequency/risk of adverse events by treatment site. Potential toxicities reported would include pneumonitis, esophagitis, chest wall pain, dermatologic toxicity, renal dysfunction, gastrointestinal toxicity including nausea, vomiting, and diarrhea, hepatotoxicity, and abdominal pain. These toxicities would be assessed according to site of irradiation by the treating physician and graded as per CTCAE 5.

A Randomized Trial of Consolidative Immunotherapy with vs without Thoracic Radiotherapy and / or Stereotactic Body Radiation Therapy (SBRT) after First-line Systemic Therapy for Metastatic NSCLC  
Wake Forest Baptist Comprehensive Cancer Center  
WFBCCC # 62718

Reference List

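### Section 14.1 leaves the randomisation stratum out of the log-rank test, gives PD-L1 of 1 to 50% no category in the Cox model, and names sites treated where the baseline site count is probably meant

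*Combined protocol and SAP*

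**What the plan says.** Section 13.1 and the Schema set the stratification: "Randomization will be stratified by number of metastatic sites (1-3, 4-6, or 7-8". The Schema adds that CNS disease treated before first-line therapy ends is still counted: "for stratification purposes this will still count as 1 site of disease".

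For the analysis, section 14.1 states "We will compare unadjusted median PFS between the 2 arms using a log-rank test" and mentions no stratification. It continues: "We will also use a proportional hazards model to compare progression-free survival between the two groups". The covariates are introduced as examples. They include "PD-L1 expression (< 1% vs > 50" (per cent) and "number of disease sites treated (1-3 sites vs 4-6 sites vs 7-8 sites".

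Section 14.2 applies the same approach to survival: "Overall survival comparison between the two randomized groups will be assessed with methods analogous to PFS described above in 13.1". The pointer to 13.1 follows the table of contents, where 13.1 is the primary analysis. In the body that text is now 14.1, and 13.1 is the sample-size section.

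For the control arm, section 3.0 says: "Patients will begin or resume maintenance immunotherapy no later than 21 days following randomization". No protocol radiation is given in that arm.

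Appendix D, completed before randomisation, records the total active sites, the extracranial sites intended for treatment, and whether CNS lesions are present and were resected or treated with radiosurgery.

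**The concern.** The analysis does not follow the randomisation in one respect, and two covariates are not defined for every patient.

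- **Stratum unused.** Stratifying the randomisation balances the arms on site count. A test that ignores the stratum leaves site-related variation in the comparison, so it loses power if site count is prognostic.
- **PD-L1 gap.** Sections 3.1 and 3.2 set no PD-L1 limit, yet the model has no place for patients from 1% to 50%. Read literally, they drop out of the adjusted PFS and OS models.
- **Sites treated.** The number treated follows from assignment and has no natural value in the control arm. The analyst would have to choose a meaning after the data are in.

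**Working it through.** **1. The plan's own figure.** Inputs from section 13.1: N = 112, 2:1, medians 8 and 15 months, two-sided alpha 0.05, 54 months of accrual, 60 months in total. Exponential PFS and uniform accrual are assumed.

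- Event probability = 1 − [exp(−6λ) − exp(−60λ)] / (54λ), with λ = ln 2 / median: 0.874 for control, 0.721 for radiation.
- Expected events = 112 × (0.874/3 + 2 × 0.721/3) = 86.5.
- Schoenfeld power = Φ(√(86.5 × 2/9) × |ln(8/15)| − 1.96) = 78.7%, within 2 points of the stated 80%.

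The design reproduces. Reading the 5 years as follow-up after the last patient would give 110 events and 87.5%, so the 60-month reading is used.

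**2. Log-rank with and without the stratum.** The documents give no stratum shares and no prognostic effect, so both are assumed. Each setting has 10,000 simulated trials, permuted blocks of 6 within the three strata, the overall control median held at 8 months, and a hazard ratio of 8/15 within strata. Monte Carlo error is about 0.4 points. Power in per cent:

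| Relative hazards (1-3 / 4-6 / 7-8) | Shares | Unstratified | Two strata (1-3, 4-8) | Three strata |
|---|---|---|---|---|
| 1 / 1 / 1 | 80/15/5 | 80.1 | 79.4 | 78.7 |
| | 60/30/10 | 80.6 | 80.0 | 79.3 |
| | 40/40/20 | 80.5 | 79.6 | 78.6 |
| 0.8 / 1.3 / 2.0 | 80/15/5 | 77.0 | 78.4 | 77.8 |
| | 60/30/10 | 75.1 | 77.3 | 77.3 |
| | 40/40/20 | 74.6 | 77.5 | 77.6 |
| 0.7 / 1.5 / 3.0 | 80/15/5 | 74.8 | 78.3 | 78.2 |
| | 60/30/10 | 70.8 | 77.0 | 77.8 |
| | 40/40/20 | 67.3 | 75.1 | 77.0 |

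- Not prognostic: two strata cost 0.6 to 0.9 points, three cost 1.3 to 1.9.
- Prognostic: two strata gain 1.4 to 7.8 points, three gain 0.8 (77.8 − 77.0) to 9.7 (77.0 − 67.3).
- Type I error of the unstratified test is 3.6 to 5.5%. It tends to be conservative when site count is strongly prognostic.
- Mean PFS events in the 7-8 stratum are 4.3 to 5.5, 8.7 to 10.7 and 17.3 to 20.8 for the three sets of shares, so that stratum may be sparse.

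**3. PD-L1.** Section 1.3 gives 28.1% of primary tumours positive at the 1% cut-off and 13.0% at the 50% cut-off. The difference is 15.1%, and 0.151 × 112 = 16.9, about 17 patients. If they dropped out, with events in proportion, 86.5 × (1 − 0.151) = 73.4 events would remain. Assumed shares of 10% and one third leave 77.9 and 57.7. As listed, the model has 10 parameters, or 11 if ECOG is categorical: treatment, age, ECOG (1 or 2), response, brain metastases, PD-L1, histology, site band (2) and time to randomisation.

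**4. Site count.** If controls are given zero treated sites, they fall in none of the three bands, and the arm indicator equals the sum of the three treated-band indicators (rank 3 of 4). The arm effect then cannot be separated from the covariate. The matching bands and the timing of Appendix D suggest the baseline stratum is meant, but 14.1 does not say so.

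The count itself is described differently: metastatic sites in the Schema and 13.1, total active sites in Appendix D. Take a patient with 3 active extracranial sites plus treated CNS disease. The Schema rule counts 3 + 1 = 4, band 4-6. The active total is 3, band 1-3, if the treated lesion is no longer active and is left out.

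**The case against.** The covariate list is illustrative, so it excludes neither the stratum nor a third PD-L1 level. Appendix D gives every patient, controls included, a pre-randomisation count of extracranial sites intended for treatment, and it records CNS disease separately. If sites treated means the baseline band, the Cox model already uses the stratum. The log-rank test is valid, and the gain from stratifying rests on inputs the documents do not give. The largest gains need a 40/40/20 split and hazards from 0.7 to 3.0.

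Much of this stands. The site-count part is mainly a wording clarification, and the size of the power gain is an assumption. What remains is that no listed PD-L1 category takes a patient from 1% to 50%, and an open list leaves that choice until after the data are seen. The stratum is also not used in the log-rank test on any reading.

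Stronger readings are tempting and should be resisted:
- That the unstratified test is invalid or the trial underpowered. The stated power reproduces, and the simulations show no material inflation of type I error.
- That the treatment effect will be biased. In an illustrative run with assumed hazards, placing all controls in the lowest treated band moved the median hazard ratio from about 0.52 to about 0.44, but nothing in 14.1 prescribes that coding.
- That a patient with only residual primary disease has no stratum. This requires metastatic sites to exclude the primary, while eligibility and Appendix D count active sites, which fits bands running from 1 to 8.

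**Conclusion.** The concern holds as a matter of specification. The log-rank test does not use the randomisation stratum. Under the assumed shares and hazards this forgoes roughly 1 to 8 power points against two pooled strata (up to about 10 against three) if site count is prognostic, and forgoes nothing if it is not. The PD-L1 coding leaves out an unknown share of eligible patients, about 17 of 112 if the background figures applied here. That loss would affect only the adjusted models; the log-rank test keeps all 112. The sites-treated wording is a definition problem, and no bias is claimed. These are changes worth making before any comparison of arms. They do not call the design into question.

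**What to change.** 1. In 14.1 and 14.2, stratify the log-rank test and the Cox models for PFS and OS by the site-count stratum recorded at randomisation. Delete the number of sites treated from the covariate list, so that the stratum is used once only; the same bands cannot also be estimated as covariates in a model stratified by them. Pooling the sparse 7-8 stratum, for example 1-3 against 4-8, is optional and must be fixed before any comparison of arms. Correct the cross-reference in 14.2 to 14.1.
2. Code PD-L1 as below 1%, 1-49%, 50% or more, and unknown. First confirm that it is collected: no reproduced form shows the field, and the content of the baseline characteristics form listed in section 10.0 (Data Management) is not shown.
3. As a clarification, use one definition of the site count in the Schema, 13.1 and Appendix D. State whether the active total includes previously treated CNS disease, which the Schema counts as 1, and how it relates to the Appendix D field for extracranial sites intended for treatment.

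**Cost.** Wording only, with no new visits or patients. As listed, the model stays at 10 or 11 parameters: PD-L1 goes from 1 to 3 and the site band from 2 to 0. The price is about 1 to 2 points of power if site count is not prognostic, and no Cox estimate of a site-count effect.

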**14.2 Analysis of Secondary Objective**

The proportions with local control (LC) of SBRT-treated lesions, and overall survival (OS) parameter estimates, both secondary outcomes, will be first examined in simple univariate and bivariate analyses (e.g., means, medians, 85% confidence intervals around key parameter estimates.). LC will be assessed only in patients with at least 4-months of radiographic follow -up. The reason for specifying a minimum of 4 months follow-up to score LC was to avoid uncertainty associated with early transient radiographic changes within the high dose region; patients who died without a minimum of 4 months post-SBRT imaging study follow-up are not considered evaluable for LC but are evaluable for PFS and OS.

Data will be collected for planned subset analysis of in-field local control of irradiated sites, progression-free and overall survival according to (1) tumor histology (adenocarcinoma vs other histology) and (2) response to initial chemotherapy (response vs stable disease).

In all randomized patients, time to progression at known sites of disease, as well as time to development of new disease sites, and number of new disease sites will be collected.

Overall survival comparison between the two randomized groups will be assessed with methods analogous to PFS described above in 13.1. Additionally, we will also examine OS in the group of patients who were enrolled but not randomized; however, we will not conduct statistical comparisons of this group with either randomized group.

All safety measures, including acute and late toxicity, will be reported using descriptive statistics (mean, median, SD, proportions, and 95% confidence intervals). This will include calculating frequency/risk of adverse events by treatment site. Potential toxicities reported would include pneumonitis, esophagitis, chest wall pain, dermatologic toxicity, renal dysfunction, gastrointestinal toxicity including nausea, vomiting, and diarrhea, hepatotoxicity, and abdominal pain. These toxicities would be assessed according to site of irradiation by the treating physician and graded as per CTCAE 5.

A Randomized Trial of Consolidative Immunotherapy with vs without Thoracic Radiotherapy and / or Stereotactic Body Radiation Therapy (SBRT) after First-line Systemic Therapy for Metastatic NSCLC  
Wake Forest Baptist Comprehensive Cancer Center  
WFBCCC # 62718

Reference List

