  - c. The schedule above is standard of care for imaging followup. Should a patient be enrolled after starting maintenance immunotherapy and after their first 3 month followup scan, then they may be allowed to switch to 6 months interval imaging at 3yrs from the end of chemo-immunotherapy, rather than a full 3 yrs from the date of randomization in accordance with standard of care. At discretion of treating oncologist.
7. Definition of 1 mo. or 30 day followup
  - a. For patients randomized to RT, this time point is considered 30 days +/- 14 days from end of all radiation therapy treatments
  - b. For patients randomized to immunotherapy alone, this time point is considered 30 days +/- 14 days from the end of the 2nd cycle of on protocol maintenance immunotherapy
8. Two tubes of whole blood may be collected at time of registration or any time prior to initiating any protocol directed therapy and at the 1 month follow up +/- 2 weeks.
9. If patients progress and are not eligible for randomization, or if they progress at any point on the study, they are only followed w appendix L for survival after the point of progression

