### For patients randomized to radiation:

Patients will undergo CT imaging of chest/abdomen/pelvis at 1 month after the last treatment of radiation is completed. Subsequently, they will undergo CT imaging of chest/abdomen/pelvis every 3 months for 3 years, then every 6 months for 2 years per standard of care.

**For patients randomized to continue maintenance immunotherapy:** alone, they will undergo CT imaging of chest/abdomen/pelvis at 1 month after the 2nd cycle of protocol directed maintenance immunotherapy has been delivered. Subsequently, they will undergo CT imaging of chest/abdomen/pelvis every 3 months for 3 years, then every 6 months for 2 years per standard of care.

Should a patient be enrolled after starting maintenance immunotherapy and after their first 3 month followup scan, then they may be allowed to

switch to 6 months interval imaging at 3yrs from the end of chemo-immunotherapy, rather than a full 3 yrs from the date of randomization in accordance with standard of care. At discretion of treating oncologist.

If a patient, has suspicion of progression but requires closer interval followup than 3 months or additional imaging, this is allowable at the discretion of the treating physician. If ultimately, they are deemed to not have progressive disease, they would then resume the schedule listed in the study calendar above.

**8.4.2** Patients who progress on or after protocol directed therapy will be followed for survival only as per Appendix L without further protocol follow up requirements. This includes progression of the protocol treated tumors, non-protocol treated tumors and the development of new metastatic disease. Tumor progression will be determined by RECIST criteria.

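### The 4-month evaluability rule can drop confirmed early in-field failures from local control, so the estimate is selected on the outcome and probably runs high

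*Combined protocol and SAP*

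**What the plan says.** Section 14.2 treats LC as a secondary outcome and plans to report "The proportions with local control (LC) of SBRT-treated lesions", with "85% confidence intervals around key parameter estimates". It gives no time point, censoring rule or competing-event rule. The population is restricted: "LC will be assessed only in patients with at least 4-months of radiographic follow"-up. The stated purpose is "to avoid uncertainty associated with early transient radiographic changes within the high dose region". One excluded group is spelled out: "patients who died without a minimum of 4 months post-SBRT imaging study follow-up are not considered evaluable for LC". Those patients stay in PFS and OS. Nothing is said about a patient whose irradiated lesion fails before month 4.

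Section 8.4.2 states: "Patients who progress on or after protocol directed therapy will be followed for survival only as per Appendix L". It adds: "This includes progression of the protocol treated tumors, non-protocol treated tumors and the development of new metastatic disease". Footnote 9 of the study calendar (8.1) repeats that after progression "they are only followed w appendix L for survival after the point of progression".

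Radiation-arm CTs are due 1 month after the last radiation treatment and then every 3 months, so nominally at months 1, 4 and 7. Footnote 7 allows 14 days either side of the 1-month visit, and 8.4.1 allows 8 weeks either side of follow-up assessments. Section 8.4 also permits extra imaging when progression is suspected.

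Three other provisions carry no 4-month limit. Appendix K records whether progression lies inside the radiation field, 8.7 allows PET to help adjudicate local failure, and 14.2 collects time to progression at known sites in all randomized patients.

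**The concern.** Read together, these rules let the failure cause the exclusion. An irradiated lesion that progresses at the 1-month CT, at a CT done early in the window, or on an unscheduled scan moves the patient to survival-only follow-up. The patient then never accrues 4 months of protocol imaging and is not evaluable for LC. The same patient is a PFS event and an in-field progression on Appendix K.

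The aim of not misreading early transient change is sound. It justifies leaving an unconfirmed enlargement unscored. It does not require dropping a failure that has been confirmed. At stake are the LC figure and the planned LC subset analyses by histology and by response to initial therapy, which inherit the same selection.

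**Working it through.** **The plan's own figures.** The plan gives no target, expected value or sample size for LC. Section 13.1 supplies only the arm size: 112 randomized 2:1 gives 112 × 2/3 = 74.7, about 75. The 112 itself is close to reproducible. With HR 0.53, 54 months of accrual and 60 months in total, it yields 86.5 expected events and power of 0.795 against the stated 0.80. Enrolment is 112/0.9 = 124.4, so 125.

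**Assumptions not in the plan for LC.** Time from end of radiation to first progression or death is exponential with median m of 11 months (a cited single-arm trial, section 1.1) to 15 months (13.1, where it is measured from the start of systemic therapy). The in-field share s of first events runs from 5% to 23% (in-field failure of 5% and 15% in two cited trials; 3 of 13 failures with a locoregional component in a third). A shorter median would raise the counts below.

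**Step 1: first events before month 4.** The count is 75 × (1 − 2^(−4/m)).
- m = 15: 75 × 0.169 = 12.7
- m = 11: 75 × 0.223 = 16.7

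In-field events among them range from 12.7 × 0.05 = 0.6 to 16.7 × 3/13 = 3.9. These are upper bounds, because an event first seen at the month-4 CT comes with 4 months of imaging.

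**Step 2: apply the scan schedule.** I used a simulation with s = 15%, 600,000 patients per scenario, the first CT at month 1 ± 14 days, and later CTs at months 4, 7 and so on. Later CTs were either exact or shifted by up to 8 weeks. Imaging stops at the scan that detects first progression.

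| Later CTs | Early in-field hazard | m | Non-evaluable of 75 | In-field failures lost |
|---|---|---|---|---|
| exact | constant | 15 | 3.4 | 0.5 |
| exact | constant | 11 | 4.6 | 0.7 |
| ± 8 weeks | constant | 15 | 6.6 | 1.0 |
| ± 8 weeks | constant | 11 | 8.8 | 1.4 |
| ± 8 weeks | doubled to month 4 | 15 | 7.6 | 2.1 |
| ± 8 weeks | doubled to month 4 | 11 | 10.0 | 2.8 |

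Unscheduled scans and deaths as first event are not modelled. Both would move the non-evaluable count towards the bound in step 1.

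**Step 3: effect on LC (%), with the ± 8 week window.** The columns are continued imaging, then imaging stopped at progression, then the stop plus the 4-month rule. Median survival of 12 months after non-local progression is assumed.

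| Early in-field hazard | m | 12 months | 24 months |
|---|---|---|---|
| constant | 15 | 92.3 / 92.6 / 93.4 | 86.5 / 89.0 / 89.5 |
| constant | 11 | 89.9 / 90.7 / 91.6 | 82.8 / 87.1 / 87.4 |
| doubled | 15 | 89.8 / 90.2 / 92.1 | 84.2 / 86.7 / 88.2 |
| doubled | 11 | 86.5 / 87.5 / 89.9 | 79.7 / 84.0 / 85.8 |
| none before month 4 | 15 | 94.9 / 95.1 / 94.7 | 88.9 / 91.4 / 90.7 |

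With constant hazard the total gap is 1.1 to 1.7 points at 12 months and 3.0 to 4.6 at 24 months. With doubled early hazard it is 2.3 to 3.4 and 4.0 to 6.1. At 24 months with constant hazard, the imaging stop accounts for 2.5 of 3.0 points (m = 15) and 4.3 of 4.6 (m = 11).

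**Step 4: direction for a crude proportion.** Treat every event before month 4 as excluded, and let e and s be the in-field shares of first events before and after month 4. Write S(t) = 2^(−t/m).
- Everyone counted, in-field failure by month t is e(1 − S(4)) + s(S(4) − S(t)).
- Under the rule it is s(S(4) − S(t))/S(4).

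The rule overstates LC only if e/s exceeds 1 − 2^(−(t−4)/m). That threshold is 0.31 (m = 15) to 0.40 (m = 11) at 12 months, and 0.93 to 0.97 at 60 months.

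**The case against.** The best defence has four parts.

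First, no CT is scheduled between months 1 and 4, so on the nominal timetable the rule removes only failures seen at the 1-month CT. This stands and is why the counts are small. The 8-week window and unscheduled imaging widen the path but do not make it large.

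Second, the planned estimator is a crude proportion over up to 5 years, and early deaths and distant progressors with controlled lesions leave the denominator too. With a constant in-field share of 15% and m = 11, the rule changes 60-month in-field failure by 0.15 × (2^(−56/11) − 2^(−60/11)) = 0.15 × (0.0293 − 0.0228), about 0.1 point. This also stands: upward bias is expected at early time points, not guaranteed, and step 4 shows when the sign reverses.

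Third, treated-site failure is captured elsewhere: on Appendix K, in secondary outcome 5.2.2 (known or new sites), in time to known-site progression, and in PFS. That is true, and it makes the correction cheap, but none of it puts the failure back into LC. Scans after progression are not forbidden, yet nothing says they are collected or count as radiographic follow-up.

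Fourth, LC is not listed among the objectives in 2.2 or the outcomes in 5.2, has no target and drives no decision. That limits the consequence without making the estimate sound.

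**Conclusion.** The point holds at modest size. As written, a confirmed in-field failure before month 4 can remove itself from LC, and the resulting estimate is selected on the outcome and probably too favourable. Under the stated assumptions about 3 to 9 of 75 radiation-arm patients become non-evaluable (10 in the most adverse scenario) and about 0.5 to 3 early in-field failures are lost. With the imaging stop, LC is overstated by roughly 1 to 5 points, and by up to 6 at 24 months if the early in-field hazard is doubled and the median is 11 months. Most of the 24-month gap comes from the imaging stop, not from the 4-month rule. The mechanism follows from the text; the size rests on the assumed exponential times and in-field shares. PFS and OS are unaffected.

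A reader might infer more, and three stronger readings are not supported:
- That every patient with an event before month 4 is excluded. The month-4 CT keeps most of them evaluable.
- That LC can be corrected by comparing failure over 12 months with failure over months 4 to 12 alone. The plan does not use that estimator, and the comparison ignores the other patients who leave the denominator.
- That LC says nothing about control of treated sites, or cannot be set beside the in-field figures in Table 1. The first overstates a shift of a few points. The second needs the cited trials' denominators, which the documents do not give.

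**What to change.** Amend the LC paragraph of 14.2 as follows:

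1. Include all irradiated patients, from the end of radiation.
2. Do not score an unconfirmed in-field change seen before 4 months. Count an in-field progression on Appendix K as an LC failure, dated to first appearance, whenever it is confirmed by PET adjudication under 8.7, by biopsy if one is done, or by further growth on a later scan.
3. Report the cumulative incidence of in-field failure, with death and out-of-field first progression as competing events. State the time points.
4. Keep the 4-month-evaluable proportion as a sensitivity analysis.

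Treating out-of-field first progression as a competing event needs no imaging after progression, so 8.4.2 and footnote 9 can stand. It does not recover in-field failures that follow an out-of-field progression, and the report should say that the estimate excludes them. Collecting in-field status after progression would instead mean changing 8.4.2 and footnote 9, and would rely on irregular routine scans.

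The cost is wording in one section, slightly more analysis work, and a somewhat less favourable LC figure. No visits, scans or forms are added.
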